6.4 Directions

IMPORTANT: Must be fasting for at least 4 hours before taking the study product.

Directions for the Investigational Group:

1. Brush teeth with tap water (no toothpaste).
2. Scrub tongue with disposable tongue scraper provided. (**Caution:** *reaching too far may cause a gag reflex.*)
3. Gargle and swish hot (optimal 120°F) water for 10-20 seconds. Spit out and repeat gargling over the next 5 minutes. The tongue should be red and without any biofilm. If it is not, repeat *Step 2*, and gargle once more.
4. Self-administer one lozenge. Let the lozenge slowly melt in the mouth. Do not chew or swallow whole. This may take up to 60 minutes. Discard if it is not fully dissolved after 60 minutes. Wait at least 30 minutes before eating your next meal.
5. Repeat *Step 1* to *Step 5* every other day for a minimum of 3 doses.
6. After the 3rd dose, you may repeat *Step 1* to *Step 5* every other day until you are satisfied with the symptom relief up to and including Day 13. Do not take the product on Day 14 onwards and return all remaining product at Visit 4.

Directions for the Control Group:

1. A box containing 8 units of the Investigational Product will be dispensed. This box will only be dispensed once, at visit 2.
2. Microwave: heat the product in 5 second increments until soft. (Caution: more than 10 seconds of microwaving the product may cause it to burn).
3. Cut: cut the product into smaller pieces those are the size of your usual medication/supplement.
4. Swallow: Participant will be instructed to swallow each of the small pieces over time with plenty of warm water. The participant will also be allowed to have a few sips of water to moisten the mouth and throat prior to swallowing the control product, if they feel it is necessary. Wait at least 30 minutes before eating your next meal. For next 2 doses, you must repeat *Step 2* to *Step 4* once every other day (day 3 and day 5).
5. After the 3rd dose, you may choose to use additional doses until you are satisfied with the symptom relief. If you choose to continue using the product, you must repeat *Step 2* to *Step 6* once every other day up to (and including) day 13. Maximum dose expected during day 1 to 13 is 7. Do not take the product on day 14 onwards and return all remaining product at visit 4.

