6.6 Blinding and Unblinding

Blinding of study products will be maintained by appropriately delegated study staff. Designated unblinded personnel will randomize the groups using block randomization ensuring an equal distribution in each group. All site staff (excluding designated unblinded personnel) will remain blinded throughout the study until the data-lock and study-closeout stage.

Since both groups will be receiving identical products (with different instructions of use for each group), emergency unblinding will not be applicable to this trial.

7. Study Design (Flow chart)

8. Planned Study Visits

Pre-Screening Telephone Call:

Potential participants who will be contacted to participate in this study will be pre-screened over the phone. They will be asked a series of questions about their health and lifestyle. As part of that telephone pre-screening the following questions will be asked regarding their allergy symptoms:

- 1- How do you score your nasal congestion (0-5, with 5 being the worst)?
- 2- How do you score your Nasal Discharge or sneezing (0-5, with 5 being the worst)?
- 3- How do you score your watery or itchy eyes (0-5, with 5 being the worst)?
- 4- How many times do you brush your teeth a day (0-3, 0,1,2,3 or more)?
- 5- How many times do you use mouthwash a day (0-2, 0,1,2 or more)?
- 6- How many times do you floss your teeth a day (0-2, 0,1,2 or more)?

Scoring Standards: Total score ≥ 7 in question 1-3 and Total score ≤ 4 in question 4-6 will be booked for Screening (V1). Potential participants with a total score of < 7 in question 1-3 and/or total score > 4 in question 4-6 will not pass the telephone pre-screening and will not be booked for Visit 1.

Visit 1 – Screening

Participants will not be required to fast prior to this visit. The delegated study staff will present the ICF, and review its contents with the participant. The study staff will answer any questions the participant may have.

The Informed Consent Form (ICF) will be provided to the participant. After a sufficient period of reflection, the written and informed consent of the participant will be sought. Each page of the ICF will be initialed and the last page will be signed by the participant. Once signed and attested to by the PI or delegate, a copy of the signed original ICF will be provided to the participant.

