10.2. Collecting, Recording, and Reporting of AEs

Collection:

The PI of delegated study staff must record all adverse events in an AE form with information about:

- Details of adverse event
- Date of onset (time can be recorded, if applicable)
- Intensity (mild, moderate, severe)
- Causal relationship to trial involvement (probable, possible, unlikely, not related)
- Other actions taken
- Date and time of outcome
- Outcome

Reporting:

The following timelines apply to the reporting of AEs/SAEs as applicable:

- Within 24 hours of the PI becoming aware of the event if it results in death of a participant

- Within 2 weeks (10 business days) after becoming aware of the event if:
 - It is an AE which is related to the conduct of the study;
 - It is an AE that is expected (listed in the ICF as a potential side effect) but is occurring more frequently than expected;
 - It is an unexpected AE/SAE that is related to the conduct of the study but is not life-threatening
- Annually (together with the Study Status Report) if:
 - It is an expected AE (listed in the ICF as a potential side effect);
 - It is an unexpected AE that is unlikely to be related to the conduct of the study and is not life-threatening.

Severity Assessment

All clinical events will be graded as mild, moderate, or severe according to the following scale:

Mild - The adverse event does not interfere in a significant manner with the subject's normal functioning level.

Moderate -The adverse event produces some impairment of functioning but is not hazardous to the subject's health.

Severe -The adverse event produces significant impairment of functioning and may be potentially hazardous to the subject's health.

Causality Assessment:

Certain – An adverse event that cannot be explained by disease or any other drugs.

Probably/Likely – An adverse event that follows a known, expected or suspected response pattern of the drug and is unlikely to be explained by any other factors or another etiology.

Possible – An adverse event that follows a known, expected or suspected response pattern of the drug but could readily have been produced by a number of other factors or explained by another etiology.

Unlikely – An adverse event that does not follow a known, expected, or suspected response pattern of the drug and could readily have been produced by a number of other factors or explained by another etiology.

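### Causality grades are defined only against the drug, although the arms differ by procedure of use, so a procedure injury has no consistent grade

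*Combined protocol and SAP*

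**What the plan says.** Section 10.2 uses two standards for causality.

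- **Grade definitions (Causality Assessment).** The top grade reads "Certain – An adverse event that cannot be explained by disease or any other drugs". The next reads "Probably/Likely – An adverse event that follows a known, expected or suspected response pattern of the drug and is unlikely to be explained by" other factors. Possible needs the same drug pattern, but with other explanations readily available. Unlikely starts "An adverse event that does not follow a known, expected, or suspected response pattern of the drug" and adds that something else could readily account for the event. Two further grades, Conditional/Unclassified and Un-assessable/Unclassifiable, depend on incomplete or contradictory information. No definition mentions the method of use or a study procedure.
- **AE form (Collection).** Staff record "Causal relationship to trial involvement (probable, possible, unlikely, not related").
- **Timelines (Reporting).** The two-week report applies to events related to study conduct. One trigger for annual reporting is "It is an unexpected AE that is unlikely to be related to the conduct of the study and is not life-threatening".

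On what differs between the arms, 6.6 says "Since both groups will be receiving identical products (with different instructions of use for each group"). Under 6.4 the investigational group brushes, scrapes the tongue, follows the step "Gargle and swish hot (optimal 120°F) water for 10-20 seconds", and lets the lozenge dissolve. The control group microwaves the product, cuts it up and swallows the pieces. Section 6.4 itself cautions about gagging with the scraper and about the product burning when over-heated. Safety is the first secondary objective (section 4).

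**The concern.** When two arms receive the same substance and differ in what participants do with it, the causality scale has to be able to attribute an event to what they do. The scale in 10.2 cannot. An assessor faced with a scald is asked whether it resembles a response to the drug, and it does not.

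At stake is the relatedness attached to harms of the randomised component, in a trial with safety as a secondary objective. If one assessor answers the form's question and another applies the written definitions, the same injury gets different grades. If all apply the definitions, such injuries tend towards the unrelated end. Blinding may add to this: under 6.5 and 6.6 most site staff do not know the assigned instructions, and participants are asked not to disclose them. An assessor who does not know which steps were performed has some reason to fall back on the drug-based text. That last step is an inference, not something the protocol states.

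**Working it through.** The plan gives no figure on this point, so the check sets the definitions side by side and applies each one as a rule.

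**Test event:** a clear procedure injury, such as a mouth scald from the gargle or an abrasion from the scraper. Its features are: no drug response pattern; not explained by disease or another drug; explained by another factor, namely the procedure; information sufficient.

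| Defined grade (10.2) | What it requires | Met? | On the AE form? |
|---|---|---|---|
| Certain | Disease and other drugs do not explain it | Yes | No |
| Probably/Likely | Drug pattern, and other causes unlikely | No | Yes (as probable) |
| Possible | Drug pattern, with other causes available | No | Yes |
| Unlikely | No drug pattern, and another cause available | Yes | Yes |
| Conditional/Unclassified | More data needed | No | No |
| Un-assessable/Unclassifiable | Information insufficient or contradictory | No | No |

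**Result 1.** The event fits 2 of 6 defined grades, and these are opposite ends of the ordered part of the scale. Certain fits only because its definition asks about disease and other drugs, and is silent on the procedure.

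**Result 2.** The form has four options. Three (probable, possible, unlikely) correspond to defined grades. The fourth, not related, has no definition. Of the two grades that the injury meets, only Unlikely can be ticked.

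**Result 3.** Answer the form's own question instead. A scald from a protocol-directed gargle plainly has to do with trial involvement, so probable is a natural entry. The same event is therefore probable on the form's question and unlikely on the only definition that label has. No text in 10.2 says which governs.

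**Result 4, timelines.** These turn on study conduct, not on the drug grade. Section 15.3 names venipuncture risks, low-grade fever, tiredness and mild headache. If the consent form matches that list, a scald is unexpected. For a non-life-threatening event of that kind, relatedness to study conduct then decides between 10 business days and the annual report. Read on its own terms, the two-week trigger captures the scald. It reaches the annual report only if the assessor carries the drug-based Unlikely across to the study-conduct question, which the text neither requires nor rules out.

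**Result 5, analysis.** Section 11.3.4 lists assessment of AEs but specifies no table by relatedness. If one were produced, 72 participants split equally gives 72 / 2 = 36 per arm, so each participant reclassified would move that arm's proportion by 1 / 36 = 2.8 percentage points. The documents give no rate for procedure injuries, so the total shift cannot be estimated.

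**The case against.** The strongest reply is that 10.2, taken as a whole, does look beyond the drug. The form asks about trial involvement, the timelines use study conduct, and 10.1 accepts that an AE may have a cause other than the drug or therapy. All AEs must be recorded, so a procedure injury stays in the data whatever its grade. This stands, and it rules out several stronger readings that a reader might infer:

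- *That causality throughout the section is judged only against the drug.* This is true of the grade definitions, not of the form or the timelines.
- *That procedure injuries move from the two-week to the annual report.* The triggers do not use the drug grade; this would take a misapplication that the text permits but does not direct.
- *That the planned safety conclusion is biased towards no related harm.* No planned analysis is shown to use the causality grade.
- *That procedure harms are the only harms that could differ between arms.* Oral exposure differs by design, with up to 60 minutes of dissolving against swallowing, and doses after the third are optional in both arms. Product effects could differ too, and the drug-based grades can capture those.

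It is also fair that some events are borderline. Throat discomfort while swallowing pieces could be read as a suspected response to the product, and the two information-based grades can apply while facts are missing. Venipuncture bruising is a weak example, since both arms have the same draws and it is a listed risk.

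What the reply does not remove is the gap between label and definition. The form's wording supplies a question but no criteria. The only criteria for probable, possible and unlikely are the drug-based ones, and for a clear procedure injury they give a different answer.

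**Conclusion.** The point holds for the grade definitions. They refer only to drugs, they conflict with the standard used by the form and the timelines in the same section, and nothing reconciles them. For a clear procedure injury, the recorded relatedness can be probable or unlikely depending on which text the assessor follows. Harms of the randomised component can therefore be understated or graded inconsistently.

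The size is qualitative: four of six defined grades cannot apply, and one of the remaining two is missing from the form. Effects on reporting time or on a related-event table are possible but conditional. The conclusion assumes a literal reading of the definitions and an injury clearly due to a step in 6.4. It does not touch the efficacy comparison. It is worth correcting because the change is small and safety is a stated objective.

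**What to change.** In 10.2, define each causality grade against *the study product, its assigned method of use, or another study procedure*. Use that one scale, with one list of categories each of which is defined, for the AE form, for deciding whether an event is related to study conduct under the reporting timelines, and for any safety summary by relatedness. Matching the form's labels to the existing definitions would not be enough, because the definitions would still refer to the drug.

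If a field for the suspected source is added to the form, word it neutrally with respect to arm (product, method of use, other study procedure), so that completing it does not reveal the allocation to blinded staff.

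The cost is a wording change in 10.2 and a matching revision of the AE form, with no change to visits or assessments. The downside is that somewhat more events will be counted as related, and some of these may fall under the two-week report.

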10.3. Serious Adverse Events

Definition:

A Serious Adverse Event (SAE) or reaction is any untoward medical occurrence that at any dose:

- Results in death;
- Is life-threatening;
- Requires inpatient hospitalization;
- Results in persistent or significant disability/incapacity or;
- Is a medical event that may jeopardize the patient/participant and may require medical or surgical intervention.

Reaction Reporting:

(1) During the course of a clinical trial, the sponsor shall notify the Minister of Health of any serious adverse reaction and any serious unexpected adverse reaction to the natural health product that has occurred inside Canada as follows:

- (a) if it is neither fatal nor life threatening, within 15 days after the day on which the sponsor becomes aware of the information; and
- (b) if it is fatal or life threatening, within seven days after the day on which the sponsor becomes aware of the information.

(2) The sponsor shall, within eight days after the day on which the Minister is notified under paragraph (1)(b), provide the Minister with a complete report in respect of that information that includes an assessment of the importance and implication of any findings made.

10.4. Laboratory Test Abnormalities

Occurrences of adverse events (serious and non-serious) will be assessed by the PI and/or delegate. For this purpose, a blood sample will be collected along with a clinical examination (to measure and assess vital signs), an interview of the participant for changes in health or concomitant medications, and a review of the participant's daily diary will be carried out to assess the occurrence of adverse events.

10.5. Treatment and Follow-Up of Laboratory Abnormalities

All events will be treated in accordance with GCP to resolution or until stabilized as deemed by the PI and/or delegate

11. Statistical Evaluation

11.1. Determination of Sample Size

Seventy-two participants will be participating in the study. The sample size was chosen based on the G*Power calculator in order to detect an effect of 0.6 (Medium effect size) considering 80% power in t tests. Parametric statistical techniques including, but not limited to t tests -

Means: Difference between two independent means (two groups) will be performed on data sets which meet all requirements for normality and variance. The application of non-parametric techniques might be used for relevant data sets. Should any of the statistical methods proposed prove unsuitable during the final analysis, more appropriate methods will be used, and any changes will be documented in the clinical study report, including the rationale for use. These include the transformation of the data (for example to a logarithmic scale) in order to satisfy model assumptions, if applicable. A p-value of < 0.05 will indicate statistical significance for all tests. An exploratory data analysis (EDA) will be performed for the exploratory study part to analyze and investigate data sets and summarize the main characteristics, employing data visualization methods.

[figure not shown]

Figure 1: Analysis: A priori: Compute required sample size.

11.2. Study Population

Intention-to-treat (ITT) analysis will be considered in this study. ITT analysis includes every subject who is randomized according to randomized treatment assignment. The ITT analysis includes all randomized patients in the groups to which they were randomly assigned, regardless of their adherence with the entry criteria, regardless of the treatment they actually received, and regardless of subsequent withdrawal from treatment or deviation from the protocol. ITT analysis reflects the practical clinical scenario because it admits noncompliance and protocol deviations. ITT analysis maintains prognostic balance generated from the original random treatment allocation and it gives an unbiased estimate of treatment effect.

11.3. Analysis Plan

11.3.1. Primary Variables

- The Total Nasal Symptoms Score (TNSS) change from the screening (V1), baseline by comparing D1(V2) and D7(V3) for each group and the differences between groups (investigational and control) will be statistically assessed.
- Peak Nasal Inspiratory Flow (PNIF) values change from the baseline by comparing D1 and D7 for each group and the differences between groups (investigational and control) will be statistically assessed.

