15.2.	Informed Consent Form.....	343
15.3.	Risks and Procedures to Minimize Risk.....	343
16.	Quality Assurance and Quality Control	35
16.1.	Auditing.....	354
16.2.	Monitoring.....	34
16.3.	Data Management.....	354
17.	References.....	37
18.	Appendix 1: Questionnaires.....	40

1. List of Abbreviations

ADA	Anti-Drug Antibodies
ADR	Adverse Drug Reaction
AE	Adverse Event
ALT	Alanine aminotransferase
ANOVA	Analysis of Variance
AST	Aspartate aminotransferase
BMI	Body Mass Index
BPM	Beats per minute
BUN	Blood urea nitrogen
CBC	Complete Blood Count
CRF	Case Report Form
CTMS	Clinical Trial Management Software
Cl	Chloride
Cr	Creatinine
eCRF	Electronic Case Report Form
EDTA	Ethylenediaminetetraacetic acid
ET	Early Termination
GCP	Good Clinical Practices
GLP	Good Laboratory Practices
GMP	Good Manufacturing Practices
GGT	Gamma glutamyl transpeptidase/transferase
h or hr	Hour
HCT	Hematocrit
Hb	Hemoglobin
HIV	Human Immunodeficiency Virus
ICF	Informed Consent Form
ICH	International Council for Harmonisation
ID	Identification
IP	Investigational Product
IRB	Institutional Review Board
IUD	Intrauterine Device
K	Potassium
Kg	kilogram
m	Meter
MCH	Mean corpuscular hemoglobin
MCHC	Mean corpuscular hemoglobin concentration
MCV	Mean corpuscular volume
Na	Sodium
NCS	Not clinically significant
OTC	Over the counter
PD	Protocol Deviation
PI	Principal Investigator
PV	Protocol Violation
RBC	Red Blood Cell
SAE	Serious Adverse Event

SAP	Statistical Analysis Plan
SOP	Standard Operating Procedure
WBC	White Blood Cell
EDA	Exploratory Data Analysis

2. Protocol Synopsis

Title: A randomized, double-blind, controlled, single-centre, 21-day study to investigate the efficacy of AllerPops to reduce nasal symptoms in adult volunteers with seasonal/year-long nasal allergies.

Phase: Phase II

Duration: Up to 30 days between Screening (V1) and Baseline (V2), and a 21-day intervention period, with dosing occurring every other day for a minimum of 3 doses, and thereafter until the participant is satisfied with the relief of the nasal allergy symptoms. The suitable season for the trial will be determined based on the seasonal variation measures.

Primary Objectives: To assess the effectiveness of AllerPops on relieving nasal symptoms compared to the control group in volunteers with seasonal/year-long allergies during the first 7 days of the 21-day intervention period.

Secondary Objective:

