11.3.3. Data Analysis

A descriptive statistics study will be performed for the primary variables. Continuous variables will be presented with the average and standard deviation or median range, as appropriate, and categorical variables will be presented as proportions. Parametric or non-parametric independent or related samples tests will be used, according to whether the distribution of the data in each variable is normal or not. A p-value < 0.05 is considered statistically significant. An EDA will be performed for the secondary variables (except safety) to analyze and investigate data sets and summarize their main characteristics, employing data visualization methods.

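### Within-arm before-after change is primary alongside the between-arm difference, no rule says which decides, and the role of screening TNSS is unclear

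*Combined protocol and SAP*

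**What the plan says.** Section 11.3.1 (Primary Variables) has two bullets. The first covers "The Total Nasal Symptoms Score (TNSS) change from the screening (V1), baseline by comparing D1(V2) and D7(V3) for each group" and, in the same sentence, the difference between arms; both are to be statistically assessed. The PNIF bullet has the same structure, with D1 as its only starting point.

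Section 11.3.3 supplies the tests: "Parametric or non-parametric independent or related samples tests will be used", depending on normality. Section 11.1 adds: "A p-value of < 0.05 will indicate statistical significance for all tests".

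The aim is comparative. The primary objective (sections 2 and 4) is symptom relief relative to the control group over the first 7 days. Section 9.5 mentions only between-group differences for TNSS. Section 11.1 sizes the trial for two independent means. By contrast, the section 4 primary endpoint is a reduction in symptoms with no comparator, and it lists TNSS at V1, V2 and V3. The secondary efficacy variables in section 11.3.2 are assessed only by comparing the arms.

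Three features bear on change without treatment. The synopsis gives "Up to 30 days between Screening (V1) and Baseline (V2), and a 21-day intervention period". The telephone pre-screen in section 8 requires "Total score ≥ 7 in question 1-3". Section 5.1 admits intermittent rhinitis, defined as lasting less than 4 weeks.

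**The concern.** A before-after test in one arm asks whether scores moved, whatever the cause. Randomisation protects only the comparison between arms. Symptoms of seasonal or intermittent rhinitis can change by themselves, and people admitted on a symptom score may score somewhat lower when measured again. Neither source of change says anything about mouth cleaning plus slow dissolution as against swallowing the same product.

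The plan gives these tests primary status and the same 0.05 threshold as the test that answers the objective, and it does not rank them. A report that follows the text could present a significant primary reduction in the investigational arm, or significance in that arm only, when the arms do not differ.

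V1 adds to the problem. If TNSS change is also tested from screening, the interval can run from Day -30 to Day 7, which is 7 - (-30) = 37 days. That is longer than an eligible intermittent episode.

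**Working it through.** **1. The plan's own figure.** Inputs from section 11.1: "Seventy-two participants will be participating in the study", chosen "in order to detect an effect of 0.6 (Medium effect size) considering 80% power in t tests". Section 6.6 gives equal allocation, so 72/2 = 36 per arm. For a two-sample t test with d = 0.6, alpha 0.05 and power 80% (noncentral t):

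- one-sided: 35.04, rounded up to 36 per arm, total 72; power at 36 per arm is 80.9%;
- two-sided: 44.6, rounded up to 45 per arm, total 90; power at 36 per arm is 70.9%.

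The 72 is therefore reproduced by a one-sided between-arm test. The text does not state sidedness and the figure is not shown, so I draw only one conclusion: the trial was sized for the between-arm comparison, not for a paired test.

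**2. Paired test in one arm under drift.** The documents give no SD of change and no expected drift. Let dz be the mean fall common to both arms, divided by the SD of the change score (assumed, 0 to 0.5), with no between-arm effect. With n = 36, the paired t statistic is noncentral t with 35 degrees of freedom and noncentrality dz × √36 = 6·dz. The two-sided 0.05 test rejects with probability p. Because the arms are independent, the investigational arm is significant and the control arm is not with probability p(1 - p).

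| dz (assumed) | 6·dz | p, investigational arm | p(1 - p) |
|---|---|---|---|
| 0 | 0 | 0.050 | 0.048 (5%) |
| 0.1 | 0.6 | 0.090 | 0.082 (8%) |
| 0.2 | 1.2 | 0.215 | 0.169 (17%) |
| 0.3 | 1.8 | 0.417 | 0.243 (24%) |
| 0.4 | 2.4 | 0.646 | 0.229 (23%) |
| 0.5 | 3.0 | 0.831 | 0.141 (14%) |

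A simulation of 20,000 trials agrees: p is 0.050, 0.415 and 0.833 at dz = 0, 0.3 and 0.5.

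**3. The between-arm test under the same drift.** In the same simulation it rejects in 4.9%, 4.9% and 5.1% of trials at dz = 0, 0.3 and 0.5. Drift common to both arms cancels.

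**4. How much drift could regression to the mean supply?** Assumptions: normal scores, the top 30% to 70% selected by telephone, and correlations between 0.4 and 0.8 among the telephone score and TNSS at V1, D1 and D7, with no real change in symptoms.

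| Change | dz | One-arm rejection |
|---|---|---|
| V1 to D7 | 0.06 to 0.45 | 7% to 74% |
| D1 to D7 | 0.03 to 0.13 | 5% to 12% |

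Under these assumptions regression to the mean alone leaves D1 to D7 at the low end of the table in step 2. The change from V1 is more exposed. Remission would add to both; rising exposure would work against both.

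**The case against.** The strongest reply is that the decisive comparison can be identified. The objective, the stated purpose of the control arm, section 9.5, the sample size and both bullets of section 11.3.1 all include or point to the between-arm difference. This stands: the correct test is in the plan, and what is missing is a statement that it decides. A reader might infer that the plan would accept a within-arm p-value, or significance in one arm only, as proof of efficacy. No sentence says so; the text merely fails to rule it out.

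A reader might also infer that scores are bound to fall because entry selects high symptoms. The documents do not support that. The telephone score is not TNSS: it has three items scored 0 to 5 (maximum 15), one of them on eye symptoms, and a cut of 7 is below half the maximum. No minimum TNSS applies at V1 or D1, and selection comes before V1, so part of any regression should have occurred by D1. The season is to be chosen from seasonal variation measures, so symptoms could be stable or rising. A fall is possible, not established.

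Nor is it settled that a change from V1 will be tested. The sentence in section 11.3.1 is garbled, and the comparison it names is D1 with D7. Section 4 lists V1 TNSS under the primary endpoint, which supports the V1 reading without settling it.

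Finally, rejecting a zero-change null when scores really did drift is not a type I error of the paired test. The error lies in attributing the change to treatment.

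**Conclusion.** The point holds as a gap in the primary analysis. Within-arm tests that do not answer the objective share primary status and the 0.05 threshold with the test that does, and no rule ranks them. V1's part in the TNSS change is ambiguous.

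The size depends on a drift that the documents do not give. Over an assumed 0 to 0.5 SD of the change score, with 36 per arm, two-sided paired tests and no between-arm effect, the investigational arm is significant in 5% to 83% of trials. Significance in that arm alone occurs in 5% to 24%. For D1 to D7 the upper figures would need real natural change as well as regression to the mean; from V1 regression alone could go further.

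A reader might take these percentages as an inflated error rate for the trial. They are not: the between-arm test stays at about 5%. They measure how often a within-arm result could be misread as an effect of the two-step method.

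**What to change.** In section 11.3.1, and in the primary endpoint wording of section 4, state that the between-arm difference in D1-to-D7 change is the only confirmatory comparison for TNSS and for PNIF. Rewrite the TNSS bullet so that D1 is its sole starting point, and keep V1 TNSS as a screening value only. Report within-arm changes descriptively, as means with 95% confidence intervals, and say that they are not evidence of efficacy. Changing section 11.3.1 alone would leave it inconsistent with section 4.

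The cost is a protocol wording amendment under section 13, best made before unblinding, and the loss of within-arm significance claims. No extra participants, visits or measurements are needed to remove the within-arm tests, since the 72 was calculated for two independent means.
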